#### 2.2.3 Exploratory objective

- To explore the potential biomarker for MGD013/brivanib alaninate and its correlation with subject safety and antitumor activity.

## 2.3 Objectives of Phase II study (Part two)

## 2.3.1 Primary Objectives

- To assess the safety of the investigational drugs in subjects with advanced HCC who have previously failed immune checkpoint inhibitor treatment;
- To assess the efficacy of the investigational drugs in subjects with advanced HCC who have previously failed immune checkpoint inhibitor treatment, with BICR-assessed ORR according to RECIST1.1 as the primary efficacy endpoint.

### 2.3.2 Secondary Objectives

- To assess the secondary efficacy endpoints of the investigational drugs in subjects with advanced HCC: BICR-assessed ORR according to irRECIST, investigator-assessed ORRs (inv-ORRs) according to RECIST 1.1 and irRECIST respectively, disease control rate (DCR), time to tumor progression (TTP), duration of response (DoR), progression-free survival (PFS), survival rate at 6, 9 and 12 months, overall survival (OS).

[figure not shown]
# 3. Study Design

### 3.1 Overall Design

This is a multicenter, open-label, Phase I/II clinical study, which will consist of two phases: the dose escalation study (Phase I) and the dose expansion study (Phase II). Phase II study will consist of two parts: Part 1 and Part 2.

## 3.1.1 Study Design of Phase I Study

Phase I study will enroll subjects with unresectable advanced HCC, intrahepatic cholangiocarcinoma and/or mixed hepatocellular-cholangiocarcinoma who have previously received at least first-line systematic treatment and recurred/not toraltable to the treatment. The dose escalation study of MGD013 monotherapy will be first conducted. After MGD013 400mg Q2w as monotherapy is clear, the dose escalation study of the combination therapy will be conducted. The schematic diagram of the study is shown as below:

### MGD013 monotherapy

In Phase I study, the dose escalation study of MGD013 monotherapy will be first conducted. After determining RP2D of MGD013 monotherapy, the dose escalation study of the combination therapy will be conducted. During dose escalation study of monotherapy, the starting dose of MGD013 will be 120 mg Q2W in single subject. If no ≥ Grade 2 drug-related adverse event occurs in the DLT observation period within 28 days after the first dose, the dose may escalate sequentially. The subsequent dose groups will adopt traditional 3+3 design. If adverse events of CTCAE Grade 2 or above related to the drug are observed in the subject of the starting dose group, the study will convert to traditional 3+3 escalation scheme, and at least another 2 evaluable subjects will be enrolled in the dose group. The dose of MGD013 monotherapy will be escalated to 240 mg Q2W, 400 mg Q2W and until 600 mg Q2W successively.

### MGD013 + Brivanib Alaninate (ZL-2301)

The combination therapy will be initiated after the MGD013 400mg Q2w is clear. The combination dose of MGD013 could be escalated to RP2D of MGD013 after determining.

Dose escalation study of the combination therapy will adopt traditional 3+3 dose escalation scheme; the dosage of Brivanib will start from 400 mg once daily (QD), and may escalate to 600 mg QD and a maximum of 800 mg QD (if possible). Two points should be noted: one is the combination dose of MGD 013 600mg Q2w +brivanib 400mg qd can be opened after both monotherapy RP2D of 600mg Q2w is determined and the starting dose of combination therapy is tolerant; the other is combination dose of MGD013 400mg Q2w + brivanib 600mg qd could be further explored once the starting dose of combination therapy is tolerant and the dose of MGD013 600mg Q2w+brivanib 400mg qd is not tolerant.

While two or more subjects experience DLT in the starting dose group of the combination therapy, the combination dose level escalation will be terminated, and Phase II dose-extension study will be conducted with MGD013 alone. Phase II dose-expansion study will be conducted with MGD013 alone.

The group of combination RP2D should enroll at least 6 evaluable subjects.

## **Definition of evaluable subject**

An evaluable subject is defined as a subject who received  $\geq 75\%$  of pre-specified total dose of MGD013 and brivanib alaninate (combination treatment cohort) within the first two cycles (28 days) and has completed primary safety evaluation, **or** experiences DLT at any time within 28 days.

A cycle lasts for two weeks (14 days) in the study, and the first two cycles are the DLT evaluation period. Provided that 3 or 6 evaluable subjects in one dose group have completed the first two cycle evaluation and the dose escalation criteria is met, subsequent dose cohort is open to enroll. There will be no intra-subject dose escalations. Unevaluable subjects in Phase I will be replaced until at least 3 evaluable subjects are enrolled in each dose group. Approximately  $30 \sim 43$  evaluable subjects will be enrolled. The total number of subjects will depend upon the number of dose levels.

Subjects will continue treatment until disease progression, death or the occurrence of intolerable toxicity, whichever comes first. MGD013 will be used for at most 48 cycles. Subjects receiving combination therapy can continue using brivanib alaninate if there is still no disease progression after discontinuing MGD013.

### 3.1.2 Dose Escalation Rules

During dose escalation study of monotherapy, the starting dose of MGD013 will be 120 mg Q2W with single subject in this dose cohort. If no  $\geq$  Grade 2 drug-related adverse events occur during the DLT observation period within 28 days after the first administration, the dose may escalate sequentially. The subsequent dose groups will adopt traditional 3+3 dose escalation scheme. If adverse events of CTCAE Grade 2 or above related to the drug are observed in the subject of the starting dose group, the study will convert to traditional 3+3 scheme for all dose groups, and at least another 2 evaluable subjects will be enrolled in starting dose group.

The study will not proceed with the 3+3 design in case of the following drug-related adverse events, that is, only one subject enrolled in the starting dose group:

- Grade 2 anemia
- Grade 2 endocrinopathy that is well controlled with hormone replacement therapy
- Grade 2 nausea, vomiting, dyspepsia, diarrhea or constipation that resolve to grade

[figure not shown]
1 or baseline within 48 hours after medical intervention

- Grade 2 fatigue that resolves to grade 1 within 4 days
- Grade 2 fever or flu-like syndrome that resolves to grade 1 or baseline within 24 hours after medical intervention
- Grade 2 infection that resolves to grade 1 or baseline within 72 hours after medical intervention
- Grade 2 lymphocytes or neutrophils decreased
- Grade 2 amylase or lipase increased that resolves to Grade 1 or baseline within 72 hours
- Grade 2 electrolyte disturbance that resolves to Grade 1 or baseline within 72 hours after medical intervention
- Grade 2 cancer pain
- Grade 2 headache, cough and shortness of breath that resolve to grade 1 or baseline within 24 hours after medical intervention

Except the starting dose group of monotherapy, other dose groups and combination therapy groups will adopt traditional 3+3 dose escalation scheme. Dose escalation follows the following principles:

- If no dose-limiting toxicity (DLT) is observed in a cohort of at least 3 evaluable subjects then dose escalation may occur;
- If one subject experiences a DLT in a group of 3 evaluable subjects, then the cohort will be expanded to include 3 evaluable subjects. If only one DLT is observed in the complete cohort of 6 evaluable subjects, then dose escalation may occur;
- If 2 or more subjects experience a DLT in a group of up to 6 subjects, dose will be deescalated to prior dose level and more subjects may be enrolled until there are 6 evaluable subjects in this dose group.
- If 2 or more subjects in the lowest-dose group experience a DLT during MGD013 monotherapy, the study will be terminated;
- If 2 or more subjects experience DLT in the starting dose group of the combination therapy (MGD013 400mg q2w+brivanib 400mg qd), the combination dose level escalation will be terminated.
- The dose of MGD013 and brivanib alaninate will not exceed 600mg Q2W and 800mg QD (monotherapy MTD).
- RP2D dose groups of the monotherapy and combination therapy should at least enroll 6 evaluable subjects.

The 3+3 dose escalation scheme is shown below.

### 3.1.3 Dose-Limiting Toxicity (DLT)

DLT was defined as the following adverse events (AEs) occurring within 4 weeks (the first 2 cycles, 28 days) after the investigational drugs which is at least possibly related to the study drugs:

- Hematologic Adverse Events:
  - Grade 4 neutropenia lasting  $\geq 5$  days;
  - Febrile neutropenia lasting > 48 hours or any febrile neutropenia with hemodynamic instability or an objective evidence of infection;
  - Grade 4 thrombocytopenia or Grade 3 thrombocytopenia with obvious hemorrhage;
  - ≥ Grade 3 haemolysis
- Non-hematological adverse events:
  - ≥ Grade 3 gastrointestinal reactions and electrolyte abnormal, e.g., nausea, vomiting, diarrhea constipation and abdominal pain that persist (more than 72 hours) despite an adequate medical intervention;
  - Sustained /repeated ≥3 grade hypertension which recurred despite sufficient medical interventions (BP ≥ 150/100 mmHg means 2 measurements taken at least 24 hours (h) apart ≥ 150/100 mmHg, taken after the subject had been seated/lying quietly for 10 minutes. At least 1 week was taken to evaluate subject's response to a change in antihypertensive medication (initiation or increase in antihypertensive medication). Once stabilized on antihypertensives, for 1 week, a subsequent episode of ≥150/100 was to be considered the "second event").
  - Other ≥ Grade 3 non-hematological toxicity, excluding:
    - Alopecia;
    - Grade 3 infusion-related reaction or cytokine release syndrome (CRS) that resolves after medical intervention within 12 hours

- Grade 3 fever that lasts < 72 hours and is not associated with hemodynamic compromise
- Grade 3 fatigue that lasts < 72 hours
- Grade 3 skin toxicity that resolves to ≤ Grade 2 within 14 days of initiation of oral corticosteroids
- Grade 3 endocrinopathy that is well controlled with hormone replacement therapy
- Grade 3 amylase or lipase increased without clinical or radiographic evidence of pancreatitis
- Grade 3 tumor inflammatory reaction (local inflammatory response at tumor or metastasis focuses attributed to an antitumor effect of drug, e.g., swelling, pain, fever) that resolves to ≤ Grade 2 within 7 days
- ➤ Grade 2 ocular pain or vision decreased that does not resolve to Grade 1 by topical therapy within 14 days, or that requires systemic treatment;
- ➤ Hepatic dose-limiting toxicity:
  - For subjects with  $\leq$  grade 2 baseline transaminases increased ( $\leq$  3 × ULN):
    - Transaminases increased  $> 8 \times$  the upper limit of normal (ULN);
    - Grade 3 elevated total bilirubin ( $> 5 \times ULN$ );
    - Transaminases increased (5 × ULN to 8 × ULN) that does not resolve to Grade 2 within 7 days and Grade 1 or baseline within 14 days. Oral steroids must be tapered to ≤ 10 mg of prednisone or equivalent dose within 14 days.
    - Increased total bilirubin (3× ULN to 5× ULN) that does not resolve to Grade 2 within 7 days and Grade 1 or baseline within 14 days. Oral steroids must be tapered to ≤ 10 mg of prednisone or equivalent dose within 14 days.
  - For subjects with Grade 2 baseline transaminases increased (3 × ULN to 5 × ULN), the DLT is defined as:
    - Elevation of one or more transaminases (> 10 × ULN) with increased total bilirubin (≥ 1 grade, for example: Grade 0 to 1, or Grade 1 to 2);
    - Elevation of one or more transaminases (> 10 × ULN) that does not recover to Grade 2 with steroids within 14 days or that requires another immunosuppressive agent.
    - Elevation of one or more transaminases ( $> 15 \times ULN$ );
    - Grade 3 increased total bilirubin ( $> 5 \times ULN$ ).
- Any other adverse events which in the judgment of the investigator required discontinuation from the study.

## **Definition of maximum tolerated dose (MTD)**

[figure not shown]
It is defined as the maximum dose at which <33% subjects suffer from DLTs; if 2 or more DLTs occur in a certain dose group, this dose is considered as intolerable, its prior dose level is defined as the maximum tolerated dose (MTD). There must be at least 6 evaluable subjects in the MTD dose group.

In Phase I dose escalation period, the **Safety Review Committee** (SRC) will decide whether to escalate to the next dose level or discontinue the escalation after reviewing the data from each dose group.

## 3.1.4 Design of Phase II study

In the Phase II dose expansion study, Part 1 will enroll two cohorts, MGD013 monotherapy and MGD013 in combination with brivanib alaninate. After determining the RP2D of MGD013 monotherapy, dose expansion study of monotherapy will be conducted **without** waiting for the completion of the dose escalation study of the combination treatment. Subjects of the combination therapy cohort will be enrolled after determining the RP2D of combination therapy in Phase I study.

### Schematic diagram of the study:

Each cohort will enroll approximately 30 evaluable advanced HCC subjects who progressed after immune checkpoint inhibitor treatment, and approximately 40 evaluable advanced HCC subjects who have not previously received immune checkpoint inhibitor treatment. The SWOG two-stage design will be employed. In the first stage, 20 advanced HCC subjects who have not previously received immune checkpoint inhibitor treatment will be enrolled. If response is observed in 3 or more subjects (according to RECIST 1.1), the enrollment of second stage will be open and an additional of 20 evaluable subjects will be enrolled. The enrollment of advanced HCC subjects who have previously received immune checkpoint inhibitor treatment will be similar, there are 2 stages for the group and the response (according to RECIST 1.1) of 1 and more out of 15 evaluable subjects at the first stage will support the decision to proceed to the second stage of subject accrual until there are 30 evaluable subjects in this group. If the response in any treatment group is found less than the above standard in the first period, the enrollment of second stage will be terminated.

In Phase II study, 2 weeks (14 days) will be defined as a cycle, and subjects will continue to receive study treatment until disease progression (according to irRECIST), death or the occurrence of intolerable toxicity (whichever comes first). MGD013 will be administered for

at most 48 cycles. If subjects do not have disease progression after discontinuing MGD013, subjects of the combination therapy group may continue brivanib alaninate.

Phase II Part 2 will expand the cohort study according to the safety and efficacy data obtained in Part 1. When at least 6 responders are observed among 30 evaluable patients (observed ORR=20%) in the post checkpoint inhibitor cohort in Part 1, the enrollment of Part 2 will be initiated. The treatment (MGD013 monotherapy or MGD013 in combination with Brivanib) that meets above criteria will proceed to Part 2. If both monotherapy and combination therapy achieve at least 6 responders in the post checkpoint inhibitor cohort, the decision of which treatment to proceed to Part 2 depends on the totality of safety and efficacy data from Part 1, and will be made by Safety Review Committee (SRC) after reviewing the data. About 120 advanced HCC subjects who have progressed following immune checkpoint inhibitor treatment will be enrolled to further assess the safety and efficacy of the study treatment. Decision on the study treatment (MGD013 monotherapy or in combination with brivanib alaninate) in Part 2 will be made by the sponsor according to the obtained data from Part 1.

The primary efficacy endpoint in Phase II study is BICR-assessed ORR according to RECIST1.1. Investigators will also evaluate objective anti-tumor efficacy and disease progression based on target lesions, non-target lesions and new lesions according to RECIST 1.1 and irRECIST criteria. The radiological responses that determine whether treatment groups in Part 1 will enter the second period after the completion of the first period of the study will be evaluated by investigators according to RECIST1.1. The subjects will be managed and evaluated for a disease progression that requires the discontinuation of the investigational drug by the investigators preferably according to irRECIST.

## 3.2 Discussion of Study Design

### 3.2.1 Dose Selection for Phase I Study

In Phase I of the study, MGD013 monotherapy dose escalation will be conducted first. MGD013 is a humanized PD-1 + LAG-3 bispecific, tetravalent diabody DART® molecule consisting of Fc domains, engineered as a hinge-stabilized IgG4 molecule and is designed to concomitantly bind PD-1 and LAG-3. As of November 2018, in the Phase I dose-escalation study (CP-MGD013-01), 36 patients with different types of solid tumors were administered MGD013 at a dose ranging from 1 mg to 1,200 mg Q2W, while single-patient dose escalation was adopted at dose levels of 1, 3 and 10 mg and 3+3 design was adopted at dose levels of 30 mg, 120 mg, 400 mg, 800 mg and 1,200 mg. They are generally well tolerated by the patients. Preliminary data indicated that the safety profile of MGD013 was similar to that of known immune checkpoint inhibitors. The common AEs included constipation, fatigue, nausea, infusion-related reaction, fever, abdominal pain, diarrhea, vomiting, chills, dyspnea, joint pain, back pain, blood creatinine increased, hyponatremia, headache, cough, rash and itching. Most treatment-related AEs were mild to moderate (i.e. Grade 1 or 2). Seven (19.4%) experienced at least one grade 3 treatment-related AE. No grade 4 or 5 treatment-related AEs occurred. Of the first 3 treated patients in the 1,200 mg dose cohort, 1 experienced a SAE and immune-mediated hepatitis meeting DLT criteria; 3 more patients were enrolled at the dose level and completed DLT evaluation period, without new DLTs; It did not reach the MTD (1,600 mg specified in the protocol), which would not be adopted. Therefore, the cohort of 1,200 mg became the maximum dose level in the study CP-MGD013-01. While evaluating the dose level of 1,200 mg in the dose escalation period, MacroGenics will further evaluate 600 mg Q2W in the dose expansion period.

MacroGenics chose 120 mg Q2W as the starting dose in HCCs for dose escalation. None of the 3 patients experienced DLT at the starting dose. As of April 1, 2019, enrollment of the

dose group of 400 mg Q2W has been started. In this study, 120 mg Q2W was also used as the starting dose in one HCC patient since it has been validated safe in overseas studies, and a dose level of 240 mg was added between 120 mg and 400 mg. If no  $\geq$  grade 2 drug-related adverse reactions occurred, it can be escalated to the next dose level. It will not be more than the RP2D (600 mg Q2W) that has been confirmed in other dose escalation studies of solid tumors for the monotherapy dose escalation.

After determining the RP2D of MGD013 monotherapy, it will be co-administered with brivanib alaninate at that RP2D. A multicenter, phase I, open-label clinical trial of brivanib alaninate (CA182002) is a dose escalation study in patients with tumors. In Part 1 of the study, the starting dose of brivanib alaninate was 180 mg, and the dose sequentially escalated to 320, 600, 800, and 1,000 mg once daily. Two DLTs (Mental disorder and grade 3 fatigue) occurred in the 1,000 mg group. Therefore, 800 mg QD was established as the maximum tolerated dose (MTD) of brivanib alaninate. 800 mg QD will be used in subsequent studies. In combination therapy of the study, the starting dose of brivanib alaninate is as low as 400 mg QD, to lower the risks of subjects. If the first dose is safe and well tolerated when in combination with MGD013, the dose may escalate sequentially to 600 mg, and 800 mg (if possible). If  $\ge 2$  patients experience a DLT in the first dose group of the combination therapy when MGD013 is administered at RP2D with brivanib alaninate (400mg OD), the dose of MGD013 will be de-escalated to the next level at which it will be combined with brivanib alaninate (400 mg QD). If there are still  $\geq$  2 DLTs, it indicates that there is a toxic multiply and the study will be terminated, and Phase II dose-extension study will be conducted with MGD013 alone.

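### Section 3.2.1 gives an opening trigger, a starting level and a two-DLT action for the combination that contradict Sections 3.1.1 and 3.1.2 and the synopsis

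*Combined protocol and SAP*

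**What the plan says.** **Section 3.2.1 (Dose Selection for Phase I Study).**
- Trigger and dose: "After determining the RP2D of MGD013 monotherapy, it will be co-administered with brivanib alaninate at that RP2D".
- The two-DLT rule applies "in the first dose group of the combination therapy when MGD013 is administered at RP2D with brivanib alaninate" at 400 mg QD.
- The action is that "the dose of MGD013 will be de-escalated to the next level at which it will be combined with brivanib alaninate (400 mg QD"). Only a second result of two or more DLTs ends the combination, after which Phase II uses MGD013 alone.
- The same section says of the monotherapy dose: "It will not be more than the RP2D (600 mg Q2W) that has been confirmed in other dose escalation studies of solid tumors".

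**Section 3.1.1 (combination paragraph), with the synopsis in agreement.**
- Trigger: "The combination therapy will be initiated after the MGD013 400mg Q2w is clear".
- 600+400 is a later level: "the combination dose of MGD 013 600mg Q2w +brivanib 400mg qd can be opened after both monotherapy RP2D of 600mg Q2w is determined". A second condition is that subjects have tolerated the first combination level. If 600+400 is not tolerated, MGD013 400 mg with brivanib 600 mg may be explored.
- Two or more DLTs in the starting group: "the combination dose level escalation will be terminated, and Phase II dose-extension study will be conducted with MGD013 alone".

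**Section 3.1.2 (Dose Escalation Rules).** The rule names the starting group and the consequence of two or more DLTs in it: "MGD013 400mg q2w+brivanib 400mg qd), the combination dose level escalation will be terminated".

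**Section 3.1.1 (monotherapy paragraph).** Combination escalation is said to follow determination of the monotherapy RP2D. The paragraph gives no combination dose and no DLT action, so it conflicts on the trigger only. The paragraph just before it, and Section 1.2.2, use clearance of 400 mg.

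**The concern.** These sentences settle three operational matters: when the combination opens, what MGD013 dose its first subjects receive, and whether it survives a failed first level. The text of 3.2.1 is phrased as instruction, not as background, and the protocol does not say which section prevails.

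The subjects have advanced liver cancer, and Section 8.4.3 says that hepatotoxicity and thyroid toxicity of the two drugs may overlap. Starting at 600+400 would omit the lower step that 3.1.1 requires first. After two DLTs, a team could cite the protocol for stopping or for retrying, and either choice would depart from another section. That choice would be made with the toxicity data already in hand.

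**Working it through.** The plan gives no figure on this point to reproduce. The check is a comparison of current text, followed by a short illustration.

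**1. Side by side**

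| Item | 3.2.1 | Synopsis, 3.1.1 (combination), 3.1.2 |
|---|---|---|
| Opens when | Monotherapy RP2D determined | MGD013 400 mg Q2W cleared (synopsis, 3.1.1) |
| First level | RP2D + brivanib 400 mg QD | 400 mg Q2W + brivanib 400 mg QD (named in 3.1.2) |
| 600+400 | First level, if the RP2D is 600 mg | Only after the 600 mg RP2D is set and the starting level is tolerated (synopsis, 3.1.1) |
| Two or more DLTs at first level | Lower MGD013 one level, keep brivanib 400 mg, retest | End combination escalation; Phase II with MGD013 alone (the last part in synopsis and 3.1.1) |

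**2. Consequence by RP2D**
- *RP2D 600 mg.* Under 3.2.1 the first 3 to 6 subjects receive 600 mg instead of 400 mg: 600/400 = 1.5, or 50% more. If that group passes, 400+400 is never tested.
- *RP2D 400 mg.* Both texts start at 400+400. After two or more DLTs, 3.1.2 stops, while 3.2.1 opens 240+400, a combination level found nowhere in 3.1.

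**3. Can the texts be reconciled?**
- Reading 3.2.1 as a rule for the later 600+400 group fails, because it refers to the first combination group, and 3.1.1 has its own follow-up (400+600) when 600+400 fails.
- The general 3+3 rule in 3.1.2 (step down to the previous level) does not help, because the same list has a specific rule for the combination starting group.

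**4. Illustration with assumed DLT rates.** The documents give no rates for the combination. Let r be the true DLT rate.
- A 3+3 group fails with probability F(r) = 1 − [(1−r)³ + 3r(1−r)²(1−r)³]. F = 0.0266, 0.0939, 0.1862, 0.2914 and 0.5057 at r = 5, 10, 15, 20 and 30%.
- The RP2D or MTD level needs at least 6 evaluable subjects (3.1.2 and the MTD definition), so the stepped-down level fails with probability G(r) = 1 − [(1−r)⁶ + 6r(1−r)⁵]. G = 0.0328, 0.1143, 0.2235, 0.3446 and 0.5798 at the same rates.

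*RP2D 600 mg, chance that the starting-level rule ends the combination.* Under 3.1.2 it is F(r at 400+400). Under 3.2.1 it is F(r at 600+400) × G(r at 400+400). In each range the first figure assumes half the rate at 400+400, the second the same rate.

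| Rate at 600+400 | 3.1.2 | 3.2.1 |
|---|---|---|
| 10% | 2.7–9.4% | 0.0939 × (0.0328 to 0.1143) = 0.3–1.1% |
| 20% | 9.4–29% | 0.2914 × (0.1143 to 0.3446) = 3.3–10% |
| 30% | 19–51% | 0.5057 × (0.2235 to 0.5798) = 11–29% |

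*RP2D 400 mg, chance that 3.1.2 stops but 3.2.1 continues* = F(r at 400+400) × [1 − G(r at 240+400)], from the same rate to half the rate at 240+400:
- 10%: 0.0939 × (0.8857 to 0.9672) = 8.3–9.1%
- 20%: 0.2914 × (0.6554 to 0.8857) = 19–26%
- 30%: 0.5057 × (0.4202 to 0.7765) = 21–39%

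**5. What depends on it.** Part 1 plans 40 + 30 = 70 evaluable subjects in the combination cohort. Stage 1 covers 20 + 15 = 35; the rest enrol only if the response thresholds are met (3.1.4).

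**The case against.** The best reply is that the governing rule is easy to identify. Section 3.1.2 is the section of escalation rules, names the dose and states the stop. The synopsis and 3.1.1 give the same stop. Section 3.2.1 is alone on the starting level and the retry, and it belongs to the discussion of design. The Amendment 1 summary, taken only as a sign of intent, points to a 400+400 start, which suggests that the sentences in 3.2.1 and the monotherapy paragraph were left over. The Safety Review Committee decides after every dose group. The chance that a cohort is really dosed under 3.2.1 may therefore be small.

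This stands as a limit on the practical risk. It does not reconcile the texts: the committee would still have two written rules for one result.

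The reply also limits the numbers. The percentages compare two complete rule sets under assumed rates and take no account of how likely it is that 3.2.1 would be followed. The 400 mg branch looks the less likely one: 3.2.1 treats 600 mg as confirmed in solid tumours, and in the first-in-human study one DLT was reported among the six subjects described at 1,200 mg, without an MTD being reached.

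**Conclusion.** Wrong as written: an internal contradiction in a dosing and stopping rule that should be corrected. Section 3.2.1 conflicts with the synopsis and Sections 3.1.1 and 3.1.2 on trigger, starting level and two-DLT action; the monotherapy paragraph of 3.1.1 conflicts on the trigger only. This rests on the text and on no assumed rate. Followed literally with an RP2D of 600 mg, 3.2.1 means a 50% higher MGD013 dose for the first 3 to 6 combination subjects. With an RP2D of 400 mg, it adds a 240+400 cohort where 3.1.2 stops.

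Three stronger conclusions that a reader might draw are not supported:
- *That subjects will start at 600+400.* Section 3.1.2 is explicit, and the committee reviews each group.
- *That the percentages are this trial's chances of a wrong decision.* They illustrate the gap between the rules at assumed rates of 10 to 30%, and the second set is conditional on an RP2D of 400 mg.
- *That 70 subjects are committed on this rule.* The cohort is up to 70, with 35 in stage 1.

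**What to change.** In the monotherapy paragraph of 3.1.1, make clearance of MGD013 400 mg Q2W monotherapy the condition for starting combination escalation, in place of determination of the RP2D.

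In 3.2.1, replace the RP2D trigger, the RP2D start and the step-down-and-retry rule with text such as:

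*The combination opens after MGD013 400 mg Q2W monotherapy is cleared and starts at MGD013 400 mg Q2W + brivanib 400 mg QD. If 2 or more subjects have a DLT at this level, combination escalation ends and Phase II is run with MGD013 alone. MGD013 600 mg Q2W + brivanib 400 mg QD opens only after the monotherapy RP2D of 600 mg Q2W is determined and the starting combination is tolerated; if 600+400 is not tolerated, 400 mg Q2W + brivanib 600 mg QD may be explored.*

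This uses only rules already in the protocol and keeps the lower starting dose. The cost is a wording change in two places, with no extra subjects or procedures.
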